#### 3.1 Primary Objective(s) & Hypothesis(es)

[figure not shown]
- 1) **Objective:** To determine the safety and tolerability of MK-4280 monotherapy (for subjects in Part A, Arm 1 and Part B, Arm 1) and to establish a maximum tolerated dose (MTD) or maximum administered dose (MAD)
- 2) **Objective:** To determine the safety and tolerability of MK-4280 in combination with pembrolizumab (for subjects in Part A, Arm 2 and Part B, Arm 2A, 2B and 2C) and to establish a preliminary recommended Phase 2 dose (RP2D) for combination therapy
- 3) **Objective:** To determine the safety and tolerability and to establish a preliminary RP2D of MK-4280 in combination with pembrolizumab and mFOLFOX7 (Arm 3) and of MK-4280 in combination with pembrolizumab and FOLFIRI (Arm 4) in subjects with MSS PD-1-treatment-naïve CRC that have received  $\leq 1$  line of prior therapy (Cohort B)
- 4) **Objective:** To determine the safety and tolerability of MK-4280 and pembrolizumab when administered as a co-formulated product (MK-4280A, Arm 5) and compare to the safety and tolerability of MK-4280 and pembrolizumab when administered sequentially (Part B subjects receiving MK-4280 800 mg plus pembrolizumab 200 mg Q3W, Arm 2C) (Cohort A)
- 5) **Objective:** To determine the safety and tolerability of MK-4280 and pembrolizumab when administered as a co-formulated product in subjects in China (MK-4280A, Arm 5, Cohort F)
- 6) **Objective:** To determine the safety and tolerability and to establish a preliminary RP2D of MK-4280 in combination with pembrolizumab and lenvatinib (Arm 6) in subjects with MSS PD-1-treatment-naïve CRC that have received 2 lines of prior therapy (Cohort G)

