## 6.0 TRIAL FLOW CHART

### 6.1 Part A - Arm 1 and Arm 2; Part B - Arm 1, Arm 2A, Arm 2B, Arm 2C, and Arm 5 Flow Chart

Treatment Cycle/Title	Screening Phase	Treatment Phase Cycle = 21 days									End of Treatment	Post Treatment Phase		
		Cycle 1				Cycles 2-4 				Cycles 5-8 	Cycle 9 and Beyond 	Discon.	Safety Follow-up Visit	Survival Follow-up 
Cycle Day	Screening (Visit 1)	1	2	8	15	1	8	15	9 weeks after 1 st dose	1	1		30 days after last dose	Every 12 weeks
Scheduling Window (Days)	-28 to -1			±3	±3		±3	±3	±7				±7	±7
Administrative Procedures														
Informed Consent 	X													
Informed Consent for Future Biomedical Research 	X													
Inclusion/Exclusion Criteria	X													
Subject Identification Card	X													
Demographics and Medical History	X													
Prior and Concomitant Medication Review	X	X	X	X	X	X	X			X	X	X	X	
Prior Oncology Treatment History	X													
MK-4280 Drug Administration (Arm 1 and Arm 2 only)		X				X				X	X			
Pembrolizumab Drug Administration  (Arm 2 only)		X				X				X	X			
MK-4280A Drug Administration (Arm 5 only)		X				X				X	X			

	Screening Phase	Treatment Phase Cycle = 21 days									End of Treatment	Post Treatment Phase		
		Cycle 1				Cycles 2-4 				Cycles 5-8 	Cycle 9 and Beyond 	Discon.	Safety Follow-up Visit	Survival Follow-up 
Treatment Cycle/Title	Screening (Visit 1)													
Cycle Day		1	2	8	15	1	8	15	9 weeks after 1 st dose	1	1		30 days after last dose	Every 12 weeks
Scheduling Window (Days)	-28 to -1			±3	±3		±3	±3	±7				±7	±7
Clinical Procedures/Assessments														
Adverse Events Monitoring	X	X	X	X	X	X	X			X	X	X	X	
Full Physical Examination	X	X 				X 				X 	X 	X	X	
Height	X													
Weight	X	X				X				X	X	X	X	
Vital Signs (respiratory rate, blood pressure, pulse, temperature) 	X	X	X	X	X	X	X			X	X	X	X	
12-Lead Electrocardiogram 	X	X 				X 							X	
ECOG Performance Status	X	X 				X 				X 	X 	X	X	
Survival Status 		<----->											X	
Efficacy Procedures/Assessments														
Tumor Imaging and irRECIST Response Assessment 	X									X 	X 	X 		

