 6. Vital signs (VS) to include temperature, pulse, respiratory rate, and blood pressure for all subjects. On Day 1 of Cycles 1-4, collect prior to dosing and at 2 hrs, 4 hrs, and 6 hrs (±10 mins for each) after start of the MK-4280 or MK-4280A infusion. Beginning with Cycle 5, collect VS predose on Day 1 of each cycle for all subjects.  
 7. Twelve-lead electrocardiogram (ECG) should be performed at screening for all subjects and repeated only for subjects in Arm 1 of Part A and Arm 5 of Part B prior to and within 30 minutes after the end of the MK-4280 or MK-4280A infusion in Cycles 1-4, and at the Safety Follow-up Visit.  
 8. Tumor imaging (computerized tomography [CT] scan or magnetic resonance imaging [MRI]) should be performed within 28 days of enrollment. Tumor imaging and response assessment are to be performed 9 weeks after first dose, then every 9 weeks until disease progression. Imaging assessments should be repeated every 9 weeks and follow calendar days and should not be adjusted for delays in cycle starts. If institutional standard of care for imaging frequency differ from these guidelines, follow the institutional standard of care after confirming with the Sponsor. The same imaging technique should be used on a subject throughout the trial. Information for disease assessments may be requested and submitted for central review.  
 9. Laboratory tests at Screening are to be performed within 7 days prior to the first dose of study treatment.  
 10. On Day 1 in Cycles 1-4, CBC with differential and the Chemistry Panel should be drawn prior to dosing.  
 11. For women of reproductive potential, a urine pregnancy test will be performed at Screening and within 72 hours of receiving the first dose of study medication. If urine pregnancy test cannot be confirmed as negative, a serum pregnancy test is required.  
 12. Thyroid function testing is to be performed starting in Cycle 1 and then every other cycle and at the post treatment Safety Follow-up Visit.  
 13. Include HCV RNA (qualitative) or Hepatitis C antibody, HBsAg, and HIV type 1 and type 2 (eg, HIV-1/2 antibody screening test and evaluation of HIV viral load as needed).  

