### **7.1.2.5 Electrocardiogram**

A 12-lead ECG will be performed by the investigator or qualified designee at the time points outlined in Section 6.0 – Trial Flow Chart.

For subjects receiving lenvatinib on Arm 6:

Complete, standardized, 12-lead ECG recordings that permit all 12 leads to be displayed on a single page with an accompanying lead II rhythm strip below the customary  $3 \times 4$  lead format are to be used. In addition to a rhythm strip, a minimum of 3 full complexes should be recorded from each lead simultaneously. Subjects must be in the recumbent position for a period of 5 minutes prior to the ECG. The Fridericia correction method for calculating QTc will be used.

An ECG abnormality may meet the criteria of an AE as described in this protocol (see Section 7.2) and the CRF Completion Guidelines. In these instances, the AE corresponding to the ECG abnormality will be recorded on the appropriate CRF.

QTc prolongation has been seen in some lenvatinib studies. Monitor electrocardiograms every cycle (as specified in Section 6.3 – Arm 6 Flow Chart) in patients with congenital long QT syndrome, congestive heart failure, bradyarrhythmias, or those who are taking drugs known to prolong the QT interval, including Class Ia and III antiarrhythmics. Refer to the lenvatinib IB.

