#### **8.4.2 Safety Endpoints**

The primary safety endpoint is DLT. Safety will be monitored by cumulative data reviews throughout the trial. The toxicities and grades experienced by subjects who have received study treatment, including AEs and SAEs, will be summarized. Of particular interest are infusion related reactions and immune-related AEs. Other safety measures evaluated in all parts of the study include laboratory safety assessments, ECGs, vital signs, and physical examinations.

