### **8.6.1 Statistical Methods for Safety Analyses**

Safety and tolerability will be assessed by clinical review of all relevant parameters including AEs, SAEs, laboratory tests, vital signs, ECG measurements, and physical examinations.

Dose limiting toxicities will be listed, and DLTs and AEs will be summarized as counts and frequencies for each MK-4280 dose level administered as monotherapy, in combination with pembrolizumab, or in combination with pembrolizumab and either mFOLFOX7, FOLFIRI or lenvatinib that had at least 3 subjects treated and listed for other dose levels. The estimate of the DLT rate among subjects treated with the preliminary RP2D and the 80% Bayesian credible interval based on a prior distribution of Beta (1,1) for the estimate will be provided.

Laboratory assessments, vital signs, and other safety endpoints will be summarized as appropriate.

In addition, the broad clinical and laboratory AE categories consisting of the percentage of subjects with any AE, a drug-related AE, an SAE, an AE that is both drug-related and serious, and who discontinued due to an AE will be summarized for dose levels with at least 3 subjects treated and listed for other doses.

Data from subjects who experienced disease progression in the Part B monotherapy arm and crossed over into the combination arm will be presented separately.

Data from subjects in Arm 3, Arm 4 and Arm 6 will be summarized separately.

The difference and 95% CI for the rates of infusion related reactions and immune related AEs between MK-4280 administered as a co-formulated product with pembrolizumab (MK-4280A, Arm 5) and MK-4280 and pembrolizumab administered sequentially (Arm 2C, equivalent dose to Arm 5) will be calculated.

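### Arm 5 has scheduled ECGs after the first dose and its comparator Arm 2C has none, so silent ECG findings are more likely to be recorded as adverse events in Arm 5

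*Combined protocol and SAP*

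**What the plan says.** Arms 2C and 5 share one schedule, Section 6.1, whose title includes "Part B - Arm 1, Arm 2A, Arm 2B, Arm 2C, and Arm 5 Flow Chart". Its footnote 7 begins: "Twelve-lead electrocardiogram (ECG) should be performed at screening for all subjects". It then limits further ECGs: they are "repeated only for subjects in Arm 1 of Part A and Arm 5 of Part B prior to and within 30 minutes after" each infusion in Cycles 1-4, with one more at Safety Follow-up. Arm 2C is not named. Section 7.1.2.5 adds nothing for that arm: "A 12-lead ECG will be performed by the investigator or qualified designee at the time points" set out in the flow chart.

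The two arms are compared by design. Objective 4 in Section 3.1 is to determine the safety of the co-formulation in Cohort A and "compare to the safety and tolerability of MK-4280 and pembrolizumab when administered sequentially", with Arm 2C as the reference. Section 8.6.1 carries this out for two event types: "The difference and 95% CI for the rates of infusion related reactions and immune related AEs between MK-4280 administered as a co-formulated product" and the sequential regimen are to be calculated. It also lists ECG measurements among the parameters for clinical review, without a between-arm ECG contrast. Section 8.4.2 says: "Other safety measures evaluated in all parts of the study include laboratory safety assessments, ECGs, vital signs, and physical examinations".

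**The concern.** In a side-by-side safety comparison, both arms should be searched for events with the same intensity. Here one arm is searched by ECG around four infusions and at follow-up, and its comparator is not. If the two presentations had identical cardiac effects, the schedule alone would still tend to produce more recorded events in Arm 5. The direction is known in advance: against the co-formulation. The plan neither mentions the difference nor says how to handle it, so an artefact of the schedule could be read as an effect of the formulation.

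**Working it through.** **Inputs.** ECG times: Section 6.1, footnote 7. Status of the Cycle 1 predose ECG: Section 6.1, footnote 5, attached to the ECG row. Subjects per arm: 40 and 40 (Section 8.9.4). The documents give no rate of ECG abnormalities and no power or precision figure for this comparison, so there is no stated figure to reproduce.

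**Step 1: count the scheduled ECGs in the first course.** For an Arm 5 subject who completes Cycles 1-4:

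- Before infusion, Cycles 1-4: 4. The first of these precedes any drug, and footnote 5 lets a screening result from the preceding 72 hours stand in for it. It is a baseline, which leaves 3.
- After infusion, Cycles 1-4: 4.
- On treatment: 3 + 4 = 7.
- Safety Follow-up: 1.
- After the first dose: 7 + 1 = 8.

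For an Arm 2C subject the count after the first dose is 0. Over 40 subjects per arm this is up to 40 × 8 = 320 against 0.

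**Step 2: see whether anything fills the gap.**

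- Section 7.1 allows unscheduled procedures in any arm when clinically necessary. That covers symptomatic events, not silent ones.
- Subjects crossing over from Arm 1 have ECGs under Section 6.4, but Section 8.6.1 presents them separately.
- The Second Course chart (Section 6.5) gives one ECG to all retreated subjects and again repeats it only in Part A Arm 1 and Part B Arm 5.

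**Step 3: see whether other surveillance differs.** In Cohort A, vital signs, laboratory safety tests and physical examinations follow the same chart in both arms. Section 7.1.2.3 applies the same 6-hour observation after the start of infusion to both. The imbalance is confined to the ECG.

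**Step 4: trace the route into the AE counts.** Section 7.2 allows an unfavourable sign to be an AE whether or not it is drug-related. Table 9 grades asymptomatic diagnostic observations as Grade 1. Table 5 lists myocarditis as an immune-related AE from Grade 1. A silent ECG finding can therefore become a counted event, although nothing makes this automatic.

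**Step 5: size.** One extra subject with an event moves a rate by 1/40 = 2.5 points. For illustration only, let p be the true proportion of subjects, equal in both arms, with a silent event that an ECG would reveal and that would be recorded as an AE. Assume full detection in Arm 5 and detection of a fraction d in Arm 2C. The expected difference due to the schedule is p(1 − d). Both p and d are assumptions, not figures from the documents.

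| Assumed p | Difference, d = 0 | Difference, d = 0.5 | Chance of at least one such event in 40 Arm 5 subjects, 1 − (1 − p)^40 |
|---|---|---|---|
| 2.5% | 2.5 points | 1.25 points | 64% |
| 5% | 5.0 points | 2.5 points | 87% |
| 10% | 10.0 points | 5.0 points | 98.5% |

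With equal schedules, d would be 1 and the expected difference 0.

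**The case against.** The strongest reply is that little of this reaches the planned contrasts. Section 8.6.1 specifies differences with confidence intervals only for infusion-related reactions and immune-related AEs. Infusion reactions are sought in both arms with the same vital signs and the same observation period, so what is left is mainly silent cardiac immune-related events. The primary endpoint is DLT, and nothing in Section 5.2.4 suggests that a low-grade ECG-only finding would by itself be one. Precision is also low: at an illustrative 10% in both arms, the half-width of a 95% interval is about 1.96 × √(2 × 0.1 × 0.9/40) = 0.13, or 13 points. Section 8.7 rules out hypothesis testing, and allocation to these arms is not randomised. All of this stands. It bounds the effect but does not remove a one-directional difference in a primary-objective comparison.

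A reader might infer three stronger things that the documents do not support.

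- **That Section 8.4.2 contradicts the schedule.** It speaks of parts of the study, not arms, and both Part A and Part B include ECGs.
- **That every abnormality on an Arm 5 ECG becomes an AE.** Section 7.2 says a sign can be an AE, and Section 7.1.2.5, writing about Arm 6, says an ECG abnormality may meet the criteria.
- **That ECG-detected events can be found in one arm only.** This is true of scheduled first-course ECGs, but unscheduled ones are allowed in Arm 2C.

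**Conclusion.** The point holds in a limited form. The first-course schedule gives 8 ECGs after the first dose per Arm 5 subject completing Cycles 1-4 and follow-up, and none in Arm 2C, while other safety surveillance in Cohort A is matched. Silent, ECG-revealed events are more likely to be recorded in Arm 5. General AE summaries are the most exposed; the infusion-reaction and immune-related AE differences are exposed less.

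The direction is against the co-formulation and the size is unknown. The range of 1.25 to 10 points in the working rests wholly on assumed p and d and should not be quoted as an estimate of bias. The firm figures are the count (8 against 0, up to 320 against 0 in total) and the 2.5 points per extra subject. This is a cheap improvement to the analysis plan, not a flaw that invalidates the comparison.

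**What to change.** In Section 8.6.1:

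- Summarise the Arm 5 scheduled-ECG data as single-arm change from baseline, with no contrast against Arm 2C.
- Keep all events in the main Arm 5 versus Arm 2C comparison. Add a sensitivity presentation of the AE, infusion-reaction and immune-related AE differences without events first detected on a protocol-scheduled ECG after the first dose.
- State the unequal ECG schedule as a limitation.

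Do not exclude such events from the main comparison. An event that would have become symptomatic in either arm might be found first by ECG in Arm 5 and dropped, but found clinically in Arm 2C and counted. That would bias the comparison in favour of the co-formulation.

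In Section 8.4.2, name the arms that have on-treatment ECGs, as a clarification. Section 8.0 already provides for documenting analysis changes in the supplemental SAP before database lock.

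The cost is one flag in the AE data, one extra table and some wording. No new procedure is needed. The change cannot recover ECGs that were not taken in Arm 2C; it only stops their absence from being mistaken for a difference between formulations.

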## 6.2 Part B - Arm 3 and Arm 4 Flow Chart

Treatment Cycle/Title	Screening Phase	Treatment Phase Cycle = 21 days														End of Treatment	Post treatment Phase			
		Cycle 1			Cycle 2 			Cycle 3 			Cycle 4 			Odd Number Cycles  (Cycle 5, 7, 9 etc.)	Even Number Cycles  (Cycle 6, 8, 10 etc.)		Discon	Safety Follow-up Visit	Survival Follow-up 	
Cycle Day	Screening	1	2	8	15	1	8	15	1	8	15	1	8	15	1	15	1	8	30 days after last dose	Every 12 weeks
Scheduling Window (Days)	-28 to -1			±3	±3		±3	±3		±3	±3		±3	±3		±3		±3		
Administrative Procedures																				
Informed Consent 	X																			
Informed Consent for Future Biomedical Research 	X																			
Inclusion/Exclusion Criteria	X																			
Subject Identification Card	X																			
Demographics and Medical History	X																			
Prior and Concomitant Medication Review	X	X	X	X	X	X	X	X	X	X	X	X	X	X	X	X	X	X		
Prior Oncology Treatment History	X																			
MK-4280 Administration		X			X		X		X		X		X		X		X			

Treatment Cycle/Title	Screening Phase	Treatment Phase Cycle = 21 days														End of Treatment	Post treatment Phase			
		Cycle 1				Cycle 2 			Cycle 3 			Cycle 4 			Odd Number Cycles  (Cycle 5, 7, 9 etc.)		Even Number Cycles  (Cycle 6, 8, 10 etc.)			Safety Follow-up Visit
Cycle Day	Screening	1	2	8	15	1	8	15	1	8	15	1	8	15	1	15	1	8	30 days after last dose	Every 12 weeks
Scheduling Window (Days)	-28 to -1			±3	±3		±3	±3		±3	±3		±3	±3		±3		±3		
Pembrolizumab Administration 		X				X			X			X			X		X			
mFOLFOX7 (Arm 3) or FOLFIRI (Arm 4) Administration		X			X		X		X		X		X		X	X	X			
Clinical Procedures/Assessments																				
Adverse Events Monitoring	X	X	X	X	X	X	X	X	X	X	X	X	X	X	X	X	X	X		
Full Physical Examination	X	X 				X 			X			X			X		X		X	
Height	X																			
Weight	X	X				X			X			X			X		X		X	
Vital Signs (respiratory rate, blood pressure, pulse, temperature) 	X	X	X	X	X	X	X	X	X	X	X	X	X	X	X	X	X	X		
12-Lead Electrocardiogram	X																			
ECOG Performance Status	X	X 				X			X			X			X		X		X	

Treatment Cycle/Title	Screening Phase	Treatment Phase Cycle = 21 days														End of Treatment	Post treatment Phase			
		Cycle 1				Cycle 2 			Cycle 3 			Cycle 4 			Odd Number Cycles  (Cycle 5, 7, 9 etc.)		Even Number Cycles  (Cycle 6, 8, 10 etc.)			Safety Follow-up Visit
Cycle Day	Screening	1	2	8	15	1	8	15	1	8	15	1	8	15	1	15	1	8	30 days after last dose	Every 12 weeks
Scheduling Window (Days)	-28 to -1			±3	±3		±3	±3		±3	±3		±3	±3		±3	±3			
Survival Status 		<----->																X		
Efficacy Procedures/Assessments																				
Tumor Imaging and irRECIST Response Assessment 		X										X 								
Laboratory Procedures/Assessments –Analysis by Local Lab																				
Complete blood count (CBC) with differential	X 	X 	X	X	X 	X		X 		X	X 	X		X 	X	X 	X	X		
PT/INR and aPTT	X 																			
Chemistry Panel	X 	X 	X	X	X 	X		X 		X	X 	X		X 	X	X 	X	X		
CEA Testing	X 	X 			X 			X 		X 				X 		X 				
Lactate dehydrogenase (LDH), gamma-glutamyl transferase (GGT)	X 	X 			X 			X 		X 				X 		X 				

Treatment Cycle/Title	Screening Phase	Treatment Phase Cycle = 21 days														End of Treatment	Post treatment Phase			
		Cycle 1				Cycle 2 			Cycle 3 			Cycle 4 			Odd Number Cycles  (Cycle 5, 7, 9 etc.)		Even Number Cycles  (Cycle 6, 8, 10 etc.)			Safety Follow-up Visit
Cycle Day	Screening	1	2	8	15	1	8	15	1	8	15	1	8	15	1	15	1	8	30 days after last dose	Every 12 weeks
Scheduling Window (Days)	-28 to -1			±3	±3		±3	±3		±3	±3		±3	±3		±3				
Pregnancy Test – Urine Serum β-human chorionic gonadotropin (β-hCG), if applicable 	X	X																		
Urinalysis	X 				X 				X 				X 			X	X			
Thyroid Function (thyroxine [T4], triiodothyronine [T3], thyroid stimulating hormone [TSH])	X	X 5			X 		X 		X 		X 		X 			X	X			
BRAF Status 	X																			
HIV, Hepatitis B and C 	X																			
Laboratory Procedures/ Assessments-Analysis to be Performed by Central Lab																				
Anti-MK-4280 Antibodies 		X			X		X		X		X		X 			X				

Treatment Cycle/Title	Screening Phase	Treatment Phase Cycle = 21 days														End of Treatment	Post treatment Phase			
		Cycle 1				Cycle 2 			Cycle 3 			Cycle 4 			Odd Number Cycles  (Cycle 5, 7, 9 etc.)		Even Number Cycles  (Cycle 6, 8, 10 etc.)			Safety Follow-up Visit
Cycle Day	Screening	1	2	8	15	1	8	15	1	8	15	1	8	15	1	15	1	8	30 days after last dose	Every 12 weeks
Scheduling Window (Days)	-28 to -1			±3	±3		±3	±3		±3	±3		±3	±3		±3				
Anti-Pembrolizumab Antibodies 		X				X			X			X				X 		X		
PK for Pembrolizumab and MK-4280 		X	X	X	X	X	X	X				X	X	X		X		X		
PK for Oxaliplatin (Arm 3) 					X															
PK for Irinotecan (Arm 4) 					X															
PK for 5-FU 					X															
Blood for DNA Correlative Studies 		X				X											X			
Blood for RNA Correlative Studies 		X				X											X			
Blood for Genetic Analysis 		X																		
Blood for Exploratory Protein Analysis (serum) 		X				X											X			

Treatment Cycle/Title	Screening Phase	Treatment Phase Cycle = 21 days														End of Treatment	Post treatment Phase			
		Cycle 1				Cycle 2 			Cycle 3 			Cycle 4 			Odd Number Cycles  (Cycle 5, 7, 9 etc.)		Even Number Cycles  (Cycle 6, 8, 10 etc.)		Discon	Safety Follow-up Visit
Cycle Day	Screening	1	2	8	15	1	8	15	1	8	15	1	8	15	1	15	1	8	30 days after last dose	Every 12 weeks
Scheduling Window (Days)	-28 to -1			±3	±3		±3	±3		±3	±3		±3	±3		±3				
Pharmacodynamic receptor availability 		X	X	X	X	X	X	X			X	X	X			X		X		
Lipase and Amylase 		X			X			X			X				X		X	X		
T-cell flow cytometry analysis 		X		X	X	X		X	X		X	X	X							
Tumor Tissue Collection																				
Archival or New Obtained Tumor Tissue 	X																			
Post Treatment Tumor Biopsy 				X																
1. Trial treatment may be administered up to 3 days before or 5 days after the scheduled Day 1 of each cycle, beginning in Cycle 3. Cycle 2 Day 1 may be administered up to 5 days after the scheduled Day 1. 2. Documented informed consent must be obtained prior to performing any protocol-specific procedure. Tests performed prior to the subject signing consent as part of routine clinical management are acceptable in lieu of a screening test if performed within the specified time frame. 3. Providing documented informed consent for Future Biomedical Research (FBR) is optional, and may be provided at any time during the subject's participation in the trial. Detailed instructions for the collection and management of FBR specimens are provided in the Procedure Manual. 4. Pembrolizumab is administered first and then, following a 30-minute interval, MK-4280 will be administered. 5. These samples and procedures required predose on Day 1 may be performed up to 72 hours prior to dosing. If Screening was performed ≤72 hours prior to dosing in Cycle 1, the results obtained at Screening can also be used for the Cycle 1, Day 1 predose values. 6. Vital signs (VS) to include temperature, pulse, respiratory rate, and blood pressure for all subjects. On Day 1 of Cycles 1-4, collect prior to dosing and at 2 hrs, 4 hrs, and 6 hrs (±10 mins for each) after start of the MK-4280 infusion. Beginning with Cycle 5, collect VS predose on Day 1 of each cycle for all subjects. 7. Tumor imaging (computerized tomography [CT] scan or magnetic resonance imaging [MRI]) should be performed within 28 days of enrollment. Tumor imaging and response assessment are to be performed 9 weeks after first dose, then every 9 weeks until disease progression. Imaging assessments should be repeated every 9 weeks and follow calendar days and should not be adjusted																				

for delays in cycle starts. If institutional standard of care for imaging frequency differ from these guidelines, follow the institutional standard of care after confirming with the Sponsor. The same imaging technique should be used on a subject throughout the trial. Information for disease assessments may be requested and submitted for central review.

8. Laboratory tests at Screening are to be performed within 7 days prior to the first dose of study treatment.
9. For women of reproductive potential, a urine pregnancy test will be performed at Screening and within 72 hours of receiving the first dose of study medication. If urine pregnancy test cannot be confirmed as negative, a serum pregnancy test is required.
10. Include HCV RNA (qualitative) or Hepatitis C antibody, HBsAg, and HIV type 1 and type 2 (eg, HIV-1/-2 antibody screening test and evaluation of HIV viral load as needed).
11. MK-4280 and pembrolizumab ADA samples (predose; all subjects) will be drawn within 24 hours prior to start of infusion on Day 1 of Cycles 1-4, 6, and 8, and every 4 cycles thereafter.
12. Pembrolizumab and MK-4280 PK samples (predose) will be drawn within 24 hours prior to start of infusion on Day 1 of Cycles 1-4, 6, 8 and every 4 cycles thereafter.
13. Postdose pembrolizumab and MK-4280 PK samples will be drawn on Day 1 of Cycles 1, 2, 4, 6, and 8 at the end of the pembrolizumab infusion (+10 minutes; pembrolizumab PK assessed alone), at the end of MK-4280 infusion (+10 minutes), and 2 hrs after the start of the MK-4280 infusion ( $\pm$ 10 minutes). Additional postdose pembrolizumab and MK-4280 PK samples in Cycles 1, 2, and 4 will be collected on Day 2 (Cycle 1 only), Day 8, and Day 15. PK samples will also be drawn at Discontinuation and at the Safety Follow-up Visit.
14. PK samples for oxaliplatin (Arm 3), irinotecan and its active metabolite SN-38 (Arm 4), and 5-FU (Arm 3 and Arm 4) will be collected pre-dose and at the end of their respective second infusions (+10 minutes, ie Day 15 of Cycle 1). Subjects must return to the study site when the 5-FU infusion ends (46-48 hours after Cycle 1 Day 15, ie on Day 17) to provide this post-infusion sample (+10 minutes).
15. Blood for correlative studies (RNA and DNA samples) and serum for exploratory protein analysis will be drawn prior to dosing on Day 1 of Cycle 1, on Day 1 of Cycle 2 (or Day 22 of Cycle 1 for subjects who do not receive a second dose of MK-4280), and at discontinuation. Detailed instructions for the collection and management of these samples are provided in the Procedure Manual.
16. This sample should be drawn for planned analysis of the association between genetic variants in DNA and drug response. If there is either a documented law or regulation prohibiting collection, or if the IRB/IEC does not approve the collection of the sample for these purposes, then this sample will not be collected at that site. If the sample is collected, leftover extracted DNA will be stored for FBR if the subject (or legally acceptable representative) provides documented informed consent for FBR. If the planned genetic analysis is not approved, but FBR is approved and consent is given, this sample will be collected for the purpose of FBR.
17. Pharmacodynamic receptor availability samples (predose) for all subjects will be drawn within 24 hours prior to start of infusion on Day 1 of Cycles 1-4, 6, 8, and every 4 cycles thereafter
18. Postdose pharmacodynamic receptor availability samples will be drawn on Day 1 of Cycles 1, 2, 4, 6, and 8 at the end of the pembrolizumab infusion (+10 minutes), at the end of the MK-4280 infusion (+10 minutes), and 2 hrs after the start of the MK-4280 infusion ( $\pm$ 10 minutes). Additional postdose pharmacodynamic receptor availability samples in Cycles 1, 2, and 4 will be collected on Day 2 (Cycle 1 only), Day 8, and Day 15. Pharmacodynamic receptor availability samples will also be drawn at Discontinuation.
19. On Day 1 in Cycles 1-4, amylase and lipase samples should both be drawn predose and repeated 4 hours ( $\pm$ 10 mins) after the start of the first infusion. Beginning with Cycle 5, amylase and lipase should be drawn predose on Day 1 for all subjects.
20. Predose T-cell flow cytometry analysis samples will be drawn from subjects within 24 hours prior to start of infusion on Day 1 of Cycles 1-4. Postdose samples will be drawn on Day 8 of Cycle 1 only and on Day 15 of Cycles 1-4. The Sponsor may direct certain sites to not perform this assessment if it is determined to be infeasible for logistical or administrative reasons.
21. Tumor tissue (archival or newly obtained biopsy) will be required at Screening for all subjects. PD-L1 testing will be performed but does not need to be completed during Screening. Prior MSI testing is required. If subjects have not had these tests previously performed, they should be performed by the local laboratory at Screening. Leftover tissue may also be saved for Future Biomedical Research if the subject provides documented informed consent for FBR.
22. Post treatment tumor biopsy is optional, but strongly encouraged, for all subjects in Cycle 1 between Day 8 and Day 15. Leftover tissue may also be saved for FBR if the subject provides documented informed consent for FBR.
23. After confirmed disease progression, or the start of new anticancer treatment; contacts are approximately every 12 weeks. Updated survival status may be requested by the Sponsor at any time during the course of the study. Upon Sponsor notification, all subjects who do not/will not have a scheduled study visit or study contact during the Sponsor-defined time period will be contacted for their survival status (excluding subjects that have a death event previously recorded).
24. For subjects with CRC only. If BRAF status is unknown at the time of screening, the site should submit sample for local testing. If local testing is not available and a subject's BRAF status is unknown, this procedure does not need to be performed.

